#### 6.1.1.3. G1T28 Dose Evaluation

[figure not shown]
Six patients will initially be enrolled into the Phase 1b, dose-finding portion of Part 1 and will receive G1T28 200 mg/m^2 in combination with standard E/P therapy (see Section 8.1). Safety and available PK parameters from this initial cohort of 6 patients during Cycle 1 will be considered in making dose escalation/de-escalation decisions (if required). If a patient is withdrawn prior to completing all assessments in Cycle 1 for reasons other than toxicity in any cohort in the Phase 1b, dose-finding portion of Part 1, the patient will be replaced. G1T28 dose evaluation criteria are listed below and are presented as a decision tree in [Figure 6-2](#). While the dose evaluation criteria below will be used to guide all dose decisions, the SMC will be responsible for all dose and cohort recommendations.

- If there is  $\leq 1$  DLT in the first cohort of 6 patients during Cycle 1 of the Phase 1b, dose-finding portion of Part 1 and the available G1T28 PK parameters are as predicted (Section 6.1.1.2), the dose-finding portion of Part 1 will end and subsequent patients will be enrolled into the Phase 2a expansion cohort of Part 1, utilizing a dose of G1T28 of 200 mg/m^2 in combination with E/P therapy.
- If there is  $\leq 1$  DLT in the first cohort of 6 patients during Cycle 1 of the Phase 1b dose-finding portion of Part 1, and the available G1T28 PK parameters suggest that the G1T28 dose needs to be escalated or de-escalated (see Section 6.1.1.2), a second cohort

of 6 patients will be enrolled at the higher or lower predicted G1T28 dose in combination with E/P therapy. For assessment of data from the second cohort enrolled in the Phase 1b dose-finding portion of Part 1, please see the decision tree in [Figure 6-2](#).

- If there is > 1 DLT in the first cohort of 6 patients during Cycle 1 of the Phase 1b dose-finding portion of Part 1 and the available G1T28 PK parameters suggest that the G1T28 dose needs to be escalated or de-escalated (ie, in order to increase or decrease the magnitude and duration of G1 cell cycle arrest of HSPCs predicted by the PK/PD model and data from the Phase 1a Study G1T28-1-01; see Section 6.1.1.2), a second cohort of 6 patients will be enrolled at the modified G1T28 dose in combination with E/P therapy. For assessment of data from the second cohort enrolled in the Phase 1b dose-finding portion of Part 1, please see the decision tree in [Figure 6-2](#).
- If there is > 1 DLT in the first cohort of 6 patients enrolled in the Phase 1b dose-finding portion of Part 1 and the available G1T28 PK parameters from these 6 patients are as predicted (Section 6.1.1.2), the dose of G1T28 should be decreased to 160 mg/m^2 and an additional 6 patients should be enrolled at the modified G1T28 dose in combination with E/P therapy. For assessment of data from the second cohort enrolled in the Phase 1b dose-finding portion of Part 1, please see the decision tree in [Figure 6-2](#).
- If there is > 1 DLT following a G1T28 dose of 160 mg/m^2 in combination with E/P therapy in the second cohort of patients and if available, PK parameters are as predicted (Section 6.1.1.2), an additional cohort of 6 patients will be enrolled at a further decreased G1T28 dose of 130 mg/m^2 in combination with E/P therapy. For assessment of data from the third cohort enrolled in the Phase 1b dose-finding portion of Part 1, please see the decision tree in [Figure 6-2](#).
- If there is > 1 DLT following the second dose reduction of G1T28 and if available, PK parameters from the third cohort are as predicted (Section 6.1.1.2), no further dose modifications will be made and the study will be terminated.
- At any time, if ≥ 2 DLTs are observed in any given cohort, further enrollment into that cohort will be stopped until the SMC can review the available data and make dose and cohort recommendations.

**Figure 6-2 G1T28 Dose Evaluation in the Phase 1b Dose-Finding Portion of Part 1**

a Assess the adjusted G1T28 dose in the next cohort of 6 patients based on DLTs and PK (if available) per the decision tree  
 b Maximum of 2 G1T28 dose reductions are allowed

All dose-escalation/de-escalation decisions will be based on Cycle 1 safety data from all patients enrolled into the cohort and available PK data and will be reviewed by a safety monitoring committee (SMC) comprised of the sponsor, medical monitor, and the principal investigator(s) to determine the next dose level. If the G1T28 dose level for a subsequent cohort is adjusted by the SMC, the SMC may also recommend that all patients currently receiving G1T28 in combination with E/P therapy should have their G1T28 dose adjusted accordingly, starting with their next scheduled cycle. Additional cohorts for the Phase 1b dose-finding portion of Part 1 will be considered based on review of the safety data from all patients enrolled into the cohort and available PK data by the SMC. The dose for Part 2 will be obtained by utilizing all available safety and available PK data from patients enrolled in Part 1. Once the dose for Part 2 has been established, additional patients will be enrolled at the selected Part 2 dose in a Phase 2a expansion cohort in Part 1 until up to a total of 24 patients (6 from the Phase 1b dose-finding portion of Part 1 and up to 18 from the Phase 2a expansion cohort) have been enrolled at that dose. The Phase 2a expansion cohort in Part 1 will complete enrollment before enrollment into Part 2 commences.

There will be no inpatient dose modifications of G1T28 in the Phase 2a expansion cohort of Part 1 and Part 2 of the study.

Each patient will be evaluated for toxicity during each cycle. The toxicity of IV G1T28 administered with E/P therapy will be assessed by the investigators using National Cancer Institute (NCI) Common Terminology Criteria for Adverse Events (CTCAE), Version 4.03.

#### 6.1.1.4. Safety Monitoring Committee

The SMC will be set up to review safety of G1T28 for all patients enrolled in the Phase 1b dose-finding portion of Part 1 of the study. The SMC will consist of the clinical investigator(s), the medical monitor, and G1 Therapeutics representatives and/or designees. During the Phase 1b dose-finding portion of Part 1, the SMC will review any DLTs, SAEs, PK, and all other available data. The committee will make recommendations for dose escalation/de-escalation based on the criteria listed in Sections 6.1.1.1 to 6.1.1.3. While the dose evaluation criteria will be used to guide all dose decisions, the SMC will be responsible for all dose and cohort recommendations, including any adjustments to the PK collection schedule. If the G1T28 dose level for a subsequent cohort is adjusted by the SMC, the SMC may also recommend that all patients currently receiving G1T28 in combination with E/P therapy should have their G1T28 dose adjusted accordingly, starting with their next scheduled cycle.

[figure not shown]
In the Phase 2a expansion cohort of Part 1, the SMC will review any SAEs, efficacy, and all other available data. The SMC may make recommendations for continuing with the Phase 2a expansion cohort in Part 1 with enrollment of up to 18 patients, or moving to Part 2 based on safety and efficacy.

#### 6.1.2. Part 2

In Part 2, eligible patients will be randomized (1:1 fashion) to G1T28 or placebo administered IV once daily on Days 1 to 3 of E/P therapy (Figure 6-3). Randomization will

be stratified by Eastern Cooperative Oncology Group (ECOG) performance status (0 to 1 versus 2). There will be no inpatient dose modifications of G1T28 in Part 2 of the study.

**Figure 6-3 Study Schema: Part 2**

E/P = etoposide + carboplatin

- a G1T28 + E/P will continue until disease progression, unacceptable toxicity, or discontinuation by the patient or investigator (eg, after completing 6 cycles). The tumor should be assessed after every even cycle using Response Evaluation Criteria in Solid Tumors (RECIST), Version 1.1. Assessments should be performed within 7 days of starting the subsequent cycle.
- b G1T28 will be administered prior to the administration of etoposide and carboplatin on Day 1 and administration of etoposide on Days 2 and 3 of 21-day cycles
- c Patients will return to the study center for a Post-Treatment Visit at 30 + 3 days after the last dose of study drug.
- d The Survival Follow-up Phase will continue until at least 50% of the patients randomized to Part 2 of the study have died.

An independent data monitoring committee (DMC) will monitor accumulating safety and disposition data approximately every 4 months during the Treatment Phase of Part 2 of the study, depending upon the enrollment rate. Details of the DMC, including objectives, composition, scope, and frequency, will be described in a DMC charter.

### 6.1.3. Criteria for Subsequent Cycles and Study Duration

In all parts of the study, study drug administration will continue until disease progression per Response Evaluation Criteria in Solid Tumors (RECIST), Version 1.1, unacceptable toxicity, withdrawal of consent, or discontinuation by investigator (eg, after completing 6 cycles), whichever occurs first. Treatment cycles will occur consecutively without interruption, except when necessary to manage toxicities or for administrative reasons as described below.

In order to start Cycle 2 and subsequent cycles as scheduled, patients should meet all of the following criteria:

- ANC  $\geq 1.5 \times 10^9/L$
- Platelet count  $\geq 100 \times 10^9/L$

- Nonhematologic drug-related toxicities (except alopecia) must be  $\leq$  Grade 1 or have returned to baseline

A delay of up to 2 weeks is permitted to allow recovery from any toxicity in order to meet the continuation criteria for organ function. If patients meet the criteria for starting the subsequent cycle as described above, a delay of up to 1 week is permitted for administrative reasons (eg, holiday, vacation, etc.). If the subsequent cycle is delayed, the patient should still complete the clinical laboratory assessments and the FACT-L and FACT-An questionnaires on the scheduled Day 1, as well as on the actual first dosing day of the next cycle. A patient will be discontinued from the study if recovery from any toxicity, in order to meet the continuation criteria for organ function, and any delay for administrative reasons requires a total delay of  $> 2$  weeks (see Section 8.4.4.2.1 and Table 8-2).

After discontinuation of study drug, patients should be strongly encouraged to complete all scheduled assessments through the end of their current 21-day treatment cycle, including the patient-reported outcome (PRO) scales; CBC assessment on Day 22; the Post-Treatment Visit; and the Survival Follow-up Phase of the study.

The G1T28-02 study will be completed when the Survival Follow-up Phase has been completed, or upon sponsor termination of the study.

The total study duration is at least 29 months.

Part 1 is expected to be approximately 18 months, assuming 12 months of accrual, 2 weeks for screening, 4.5 months of treatment (assuming 6 cycles), and 1 month of safety follow-up.

Part 2 will begin after the Part 2 dose is identified from the Phase 1b dose-finding portion of Part 1 and the Phase 2a expansion portion of Part 1 has completed enrollment, which is expected to occur approximately 12 months after Part 1 begins. Part 2 is expected to be approximately 17 months, assuming 11 months of accrual, 2 weeks of screening, 4.5 months of treatment (assuming 6 cycles), and 1 month of safety follow-up.

The Survival Follow-up Phase of the study will continue until at least 50% of the randomized patients in Part 2 have died.

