### **Criteria for Subsequent Cycles and Study Duration**

In both parts of the study, study drug administration will continue until disease progression per Response Evaluation Criteria in Solid Tumors (RECIST), Version 1.1, unacceptable toxicity, withdrawal of consent, or discontinuation by investigator (eg, after completing 6 cycles), whichever occurs first. Treatment cycles will occur consecutively without interruption, except when necessary to manage toxicities or for administrative reasons as described below.

In order to start Cycle 2 and subsequent cycles as scheduled, patients must have an ANC  $\geq 1.5 \times 10^9/L$ , platelet count  $\geq 100 \times 10^9/L$ , and nonhematologic drug-related toxicities (except alopecia) must be  $\leq$  Grade 1 or have returned to baseline. A delay of up to 2 weeks is permitted to allow recovery from any toxicity in order to meet the continuation criteria for organ function. If patients meet the criteria for starting the subsequent cycle as stated in Section 6.1.3, a delay of up to 1 week is permitted for administrative reasons (eg, holiday, vacation, etc.). If the subsequent cycle is delayed, the patient should still complete the clinical laboratory assessments and the FACT-L and FACT-An questionnaires on the scheduled Day 1, as well as on the actual first dosing day of the next cycle. A patient will be discontinued from the study if recovery from any toxicity, in order to meet the continuation criteria for organ function, and any delay for

---

---

administrative reasons requires a total delay of > 2 weeks.

After discontinuation of study drug, patients should be strongly encouraged to complete all scheduled assessments through the end of their current 21-day treatment cycle, including the patient-reported outcome (PRO) scales; CBC assessment on Day 22; the Post-Treatment Visit; and the Survival Follow-up Phase of the study, which is to continue until at least 50% of the patients randomized to Part 2 of the study have died. The G1T28-02 study will be completed when the Survival Follow-up Phase has been completed, or upon sponsor termination of the study.

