## 8. TREATMENTS

### 8.1. Treatments Administered

The initial group of patients in Part 1 of the study will receive G1T28 200 mg/m^2 administered IV once daily on Days 1 to 3 of each 21-day E/P chemotherapy cycle. All dose escalation/de-escalation decisions and additional cohorts of patients to be enrolled in the Phase 1b dose-finding portion of Part 1, if any, will be based on Cycle 1 safety and available PK data (see Section 6.1.1). If the G1T28 dose level for a subsequent cohort is adjusted by the SMC, the SMC may also recommend that all patients currently receiving G1T28 in combination with E/P therapy should have their G1T28 dose adjusted accordingly, starting with their next scheduled cycle.

Patients enrolled to the Phase 2a expansion portion of Part 1 and Part 2 will receive the dose of G1T28 derived from the Phase 1b dose-finding portion of Part 1 or placebo administered IV once daily on Days 1 to 3 of each 21-day E/P chemotherapy cycle. There will be no inpatient dose modifications of G1T28 in the Phase 2a expansion portion of Part 1 and Part 2 of the study.

Patients will receive standard E/P chemotherapy in 21-day cycles. The carboplatin dose will be calculated using the Calvert formula with a target AUC = 5 (maximum 750 mg) IV on Day 1, and 100 mg/m^2 etoposide will be administered IV daily on Days 1, 2, and 3 of each 21-day cycle.

**The interval between doses of G1T28 or placebo on successive days should not be greater than 28 hours. The interval between the dose of G1T28 or placebo and the first dose of chemotherapy on a given day (etoposide or carboplatin) should not be greater than 4 hours.**

**G1T28 or placebo will only be administered with E/P therapy. If administration of E/P therapy is discontinued, G1T28 or placebo will also be discontinued.**

**Chemotherapy cannot be administered until after completion of the G1T28 or placebo infusion. If the second or third dose of G1T28 or placebo in any given cycle is not administered for any reason, do not administer the dose of etoposide chemotherapy on that day, since this could potentially exacerbate myelosuppression (see Section 8.4.4.1).**

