Study drug administration will continue until disease progression, unacceptable toxicity, withdrawal of consent, or discontinuation by investigator (eg, after completing 6 cycles), whichever occurs first. Treatment cycles will occur consecutively without interruption, except when necessary to manage toxicities or for up to a 1 week delay for administrative reasons, for a maximum total delay of up to 2 weeks. If the subsequent cycle is delayed, the patient should still complete the clinical laboratory assessments and the FACT-L and FACT-An questionnaires on the scheduled Day 1, as well as on the actual first dosing day of the next cycle.

Patients should meet the laboratory parameter requirements outlined in Section 10.4 before initiation of Cycle 2 and each subsequent cycle of E/P therapy. All nonhematologic

drug-related toxicities (except alopecia) should have resolved to Grade 1 or baseline before initiation of the next cycle of E/P therapy.

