##### 8.4.4.2. Modification of Etoposide and Carboplatin Dosing

Patients should meet the laboratory parameter requirements outlined in Section 10.4 before initiation of Cycle 2 and each subsequent cycle of E/P therapy. All nonhematologic drug-related toxicities (except alopecia) should have resolved to Grade 1 or baseline before initiation of the next cycle of E/P therapy.

Dose adjustments are to be made according to the organ system showing the greatest degree of drug-related toxicity. Toxicities will be graded using NCI CTCAE, Version 4.03. Initiation of the next cycle of E/P therapy may be delayed by no more than 2 weeks to allow recovery from toxicity due to the chemotherapy agents. A treatment delay of > 2 weeks due to toxicity will lead to discontinuation of E/P therapy.

No more than 2 dose reductions in total are allowed for any patient. Simultaneous reduction in the doses of etoposide and carboplatin will count as 1 dose reduction. Toxicity that requires dose reduction more than twice will lead to discontinuation of E/P therapy. Under this circumstance, administration of G1T28 should also be discontinued. All dose reductions are permanent and no dose increases are allowed.

Since fatigue can be a symptom of cancer progression, dose reduction will only be performed if it is deemed to be drug-related in the opinion of the investigator.

The dose reductions in [Table 8-1](#) will be utilized for the purpose of dose modifications for toxicity.

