### Dose Modifications for Hematologic Toxicity

#### First Day of Cycle 2 and Beyond

In order to start Cycle 2 and subsequent cycles as scheduled, on Day 1 of the cycle, patients must have an ANC  $\geq 1.5 \times 10^9/L$ , platelet count  $\geq 100 \times 10^9/L$ , and nonhematologic drug-related toxicities (except alopecia) must be  $\leq$  Grade 1 or have returned to baseline. The dose adjustments in [Table 8-2](#) are based on the ANC and platelet counts on the first day of treatment for Cycle 2 and each subsequent cycle.

**Table 8-2 Etoposide and Carboplatin Dose Adjustments Based on Lack of Recovery of Absolute Neutrophil or Platelet Counts on the First Day of Cycle 2 and Each Successive Cycle**

Absolute Neutrophil Count <math>1.5 \times 10^9/L</math>	Etoposide	Carboplatin
First episode	No change. Use G-CSF with subsequent cycles. Refer to the American Society of Clinical Oncology (ASCO) guidelines (Smith 2006).	No change. Use G-CSF with subsequent cycles. Refer to ASCO guidelines (Smith 2006).
Second episode	First dose reduction	First dose reduction
Third episode	Second dose reduction	Second dose reduction
Fourth episode	Discontinue drug	Discontinue drug
Platelet Count <math>100 \times 10^9/L</math>	Etoposide	Carboplatin
First episode	First dose reduction	First dose reduction
Second episode	Second dose reduction	Second dose reduction
Third episode	Discontinue drug	Discontinue drug

G-CSF = granulocyte colony-stimulating factor

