8.4.4.2.1. Dose Modifications for Nonhematologic Toxicity

Hepatic Toxicity

The following dose adjustments for E/P are based on serum AST/ALT and bilirubin levels ([Table 8-5](#)) during the preceding treatment cycle.

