- o Patients enrolled in Cohort 1 of the Phase 1b dose-finding portion of Part 1 will have G1T28, etoposide, and carboplatin PK samples collected on Days 1 and 3 (as applicable) of Cycle 1 at the time points specified in Section 11.2. Collection of PK blood samples from patients enrolled in additional cohorts of the Phase 1b dose-finding portion of Part 1 is optional.

- p G1T28 or placebo will be administered as an IV infusion in 250 mL of D5W or sodium chloride solution 0.9% over 30 minutes prior to E/P chemotherapy on Days 1 to 3 of every cycle (see Section 8.1). If there is any volume remaining in the G1T28 or placebo infusion bag at the end of the 30 minutes, the infusion should be continued at the same rate until the entire contents of the bag have been administered to ensure patients receive the full dose. The interval between doses of G1T28 or placebo on successive days should not be greater than 28 hours. The interval between the dose of G1T28 or placebo and the first dose of chemotherapy on a given day (etoposide or carboplatin) should not be greater than 4 hours. G1T28 or placebo will only be administered with E/P therapy. If administration of E/P therapy is discontinued, G1T28 or placebo should also be discontinued. Chemotherapy cannot be administered until after completion of the G1T28 or placebo infusion. If the second or third dose of G1T28 in any given cycle is not administered for any reason, do not administer the dose of etoposide or carboplatin chemotherapy on that day (see Section 8.1). After discontinuation of study drug, patients should be strongly encouraged to complete all scheduled assessments through the end of their current 21-day treatment cycle, including the patient-reported outcome (PRO) scales; CBC assessment on Day 22; the Post-Treatment Visit; and the Survival Follow-up Phase of the study.
- q Patient-reported outcomes should be completed at Days 1 and 10 of each cycle and at the Post-Treatment Visit. If a cycle is delayed, the patient should still complete the PRO on the scheduled Day 1 of the next cycle, as well as the actual first dosing day of the next cycle of G1T28 or placebo + E/P therapy. Patient-reported outcomes may be obtained up to 24 hours prior to the first dose of each cycle of G1T28 or placebo + E/P therapy.

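### A total cycle delay of more than 2 weeks takes the patient out of the study in five places, but only off treatment in Protocol 8.4.4.2

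*Protocol*

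**What the plan says.** Protocol 6.1.3 says "A patient will be discontinued from the study if recovery from any toxicity, in order to meet the continuation criteria for organ function", with any administrative delay added, needs more than 2 weeks in total. The sentence also stands in the synopsis ("A patient will be discontinued from the study if recovery from any toxicity"), in 10.4 and in 10.5, and SAP 2.2 restates it. In 6.1.3 it refers the reader to section 8.4.4.2.1 and Table 8-2.

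Protocol 8.4.4.2 says: "A treatment delay of > 2 weeks due to toxicity will lead to discontinuation of E/P therapy". Section 8.1 adds: "If administration of E/P therapy is discontinued, G1T28 or placebo will also be discontinued". Section 8.1 also allows treatment cycles to be held for toxicity or administrative reasons "for a maximum total delay of up to 2 weeks", without saying what happens beyond that.

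On follow-up, footnote p of Table 9-1 says: "After discontinuation of study drug, patients should be strongly encouraged to complete all scheduled assessments", and goes on to the Post-Treatment Visit and the Survival Follow-up Phase. Similar text stands in 10.8 and 12.3, and directly after the delay sentence in the synopsis, 6.1.3 and 10.5. Section 10.6 moves patients into survival follow-up once the Post-Treatment Visit is done. Section 10.7 provides monthly calls and 2-monthly scans, with no exception for patients stopped because of a delay.

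**The concern.** Leaving the study and stopping treatment are different states in this plan. Protocol 12.3 deals with stopping study drug and 12.4 with withdrawal from the study. SAP 6.2.1 counts the two separately and sets study discontinuation against continuing in survival follow-up. The delay sentence assigns the first state, while 8.4.4.2 assigns the second to a patient whose toxicity delay meets both rules.

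The main thing at stake is overall survival. It is a secondary objective, a listed safety endpoint (Protocol 13.5.1), and is compared between the Part 2 arms (SAP 6.2.8.8). If a site ended contact when the delay limit was exceeded, SAP 5.2.8 would censor the patient at the date last known alive. Patients removed this way would include a group selected by unrecovered toxicity, and hematologic toxicity is what G1T28 is meant to reduce. The censoring could therefore be informative, and its frequency could differ between arms. Scans until progression would stop as well.

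**Working it through.** No figure in the plan has to be reproduced. The check sets the rules side by side, then works out the timing.

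**1. Consequence stated for a delay of more than 2 weeks**

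| Place | Delay covered | Consequence |
|---|---|---|
| Protocol synopsis, 6.1.3, 10.4, 10.5; SAP 2.2 | Toxicity plus administrative, total | Patient leaves the study |
| Protocol 8.4.4.2 | Toxicity | E/P therapy ends; G1T28/placebo too, through 8.1 |
| Protocol 8.1 | Toxicity plus administrative, total | None stated |

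That is four protocol places and one SAP restatement against one section. For a toxicity delay beyond 2 weeks both rules apply and disagree.

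**2. Mixed delay.** As an illustration (the split is not from the documents), take 10 days for toxicity and the permitted 7 administrative days: 10 + 7 = 17 days, and 17 > 14. The total limit is exceeded. The toxicity part is 10 ≤ 14, so 8.4.4.2 is not triggered, and 8.1 states no consequence. Leaving the study is then the only consequence stated.

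**3. Timing in a fully dosed cycle.** The inputs are the last dose on Day 3, 30 days of AE reporting, a Post-Treatment Visit at 30 days (+ 3), and a 21-day cycle.

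- AE reporting ends and the Post-Treatment Visit falls due: 3 + 30 = Day 33.
- Latest day for that visit: 33 + 3 = Day 36.
- Next cycle due: Day 22. Two-week limit: 22 + 14 = Day 36.

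If the site waits out the full 2 weeks, the limit passes after Day 36. By then the AE period has ended and the visit window has closed. A literal exit at that point would stop mainly the survival calls, the 2-monthly scans and the Part 2 blood sample 60 days after the visit. The Post-Treatment Visit itself may not have taken place, because the patient was still waiting to restart.

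The rule, however, turns on whether recovery requires more than 2 weeks, and that can be judged earlier. Judged on Day 22, for example, the AE period would still have 33 − 22 = 11 days to run.

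**4. Cross-reference in 6.1.3.** Section 8.4.4.2.1 is headed "Dose Modifications for Nonhematologic Toxicity", and Table 8-2 deals with lack of count recovery on Day 1 of a cycle. Together they could be meant to cover any toxicity, but neither states the 2-week limit. For toxicity delay, that limit is in 8.4.4.2.

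**The case against.** The strongest reply is that the protocol largely resolves the conflict itself. A patient over the delay limit is necessarily off study drug, so footnote p, 10.8 and 12.3 already cover that patient without naming the reason. In three of the four protocol places the next paragraph encourages follow-up through the survival phase. Section 10.6 is unconditional, 10.7 makes no exception, and 12.4 does not list delay among the reasons for withdrawal. The SAP 6.2.1 category is a label in a disposition table and tells no site to stop calling patients.

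Most of this stands, and it is why a literal exit is unlikely. It does not remove the fault. The follow-up paragraphs apply to patients who stop study drug, and a site can consistently read them as meant for those who stay in the study. Section 10.4, where the rule first operates, has no such paragraph beside it. The list in 12.4 is expressly not exhaustive. For a mixed delay, no other consequence is stated anywhere.

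A reader might also take the entry "Discontinue drug" in Table 8-2 as showing what a long delay was meant to lead to. It does not: that entry follows a third platelet episode or a fourth neutrophil episode, and does not depend on the length of a delay.

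**Conclusion.** The sentence is wrong as written, and the fault is minor. That treatment discontinuation with continued follow-up was intended is an inference, though a well-supported one. Harm requires a site to follow this one sentence over 10.6, 10.7, 10.8, 12.3 and footnote p. The documents give no rate for delays beyond 2 weeks, so neither the number of patients affected nor any imbalance between arms can be derived.

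Three stronger conclusions that a reader might draw are not supported:

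- **That the Part 2 survival comparison is biased.** The wording opens a route to informative censoring; nothing shows that it would be taken, or how often.
- **That PFS is out of reach because it is already censored when treatment stops.** Table 18 in SAP 5.2.7 uses the last progression assessment without progression, not the stopping date, and SAP 5.2.6 continues scans every 2 months in follow-up. Lost scans could therefore matter for PFS.
- **That AE reporting is always complete before the rule applies.** This holds only if the site waits out the full 2 weeks in a fully dosed cycle.

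**What to change.** Keep the 2-week limit and make these changes:

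1. In the synopsis, 6.1.3, 10.4, 10.5 and SAP 2.2, change the consequence to *discontinued from study treatment (G1T28/placebo and E/P therapy)*.
2. Extend 8.4.4.2 to total delay, toxicity plus administrative.
3. Point the cross-reference in 6.1.3 to 8.4.4.2.
4. Add to 10.8: *Patients taken off study treatment because the total cycle delay exceeds 2 weeks complete the Post-Treatment Visit if not already done (as soon as possible if its window has passed), then have scans until progression and survival follow-up, unless consent is withdrawn.*

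The cost is wording in four protocol places and one SAP place, one line in 8.4.4.2, one reference and one sentence in 10.8. No visits, samples or calls are added to those already planned; at most, a Post-Treatment Visit takes place after its window.
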